## I. Background and Significance

Metabolic abnormalities and body composition changes are associated with combination antiretroviral therapy (cART) in HIV-infection. Recent studies have shown that hypertension [1], impaired glucose tolerance [2], Type 2 diabetes [3, 4], increased carotid intima-media thickness (cIMT) [5] as well as coronary atherosclerosis [6] and myocardial infarction [7] are more prevalent in HIV-infected individuals than in non-infected controls. Visceral adipose tissue (VAT) is increased in HIV-infected patients compared to non-infected controls [8] and is associated with cardiac risk factors such as decreased insulin sensitivity [9, 10], hypertriglyceridemia and low HDL [11], increased systemic inflammatory markers [12-14], and increased subclinical atherosclerosis [15]. At this time there is no standard of care to adequately treat these abnormalities.

The etiology of body composition changes, metabolic abnormalities, and increased cardiovascular risk is multifactorial and likely includes perturbation of multiple endocrine axes. In non-HIV-infected individuals, recent data has shown that aldosterone, a mineralocorticoid hormone, is increased in association with increased VAT [16] and decreased insulin sensitivity [17]. We have demonstrated increased 24-hour urine aldosterone in HIV-infected women with increased visceral fat accumulation, compared to age and BMI-matched healthy controls [18]. Urinary aldosterone secretion was strongly related to VAT in this study. In addition, we also observed an independent relationship between increased urinary aldosterone and hemoglobin A1c, which was independent of BMI or visceral adiposity. Furthermore, emerging animal and human studies have suggested effects of mineralocorticoid blockade on insulin sensitivity, inflammation, and hepatosteatosis [19, 20].

### ***Physiology of aldosterone and the mineralocorticoid receptor***

Recent data suggest that aldosterone and mineralocorticoid receptor (MR) activation may play a role in cardiovascular and metabolic disease [21, 22]. *In vitro* studies demonstrate effects of aldosterone on adipocyte differentiation, adipocytokine production, lipid metabolism, and insulin signaling. The physiologic relevance of these *in vitro* effects is unclear based on our current understanding of aldosterone's mechanism of action. The mineralocorticoid receptor, which is the only identified receptor for aldosterone to date, has equal affinity for aldosterone and cortisol. Certain tissues, including kidney, colonic epithelium, vascular smooth muscle [23], and endothelium [24], highly express 11 $\beta$  hydroxysteroid dehydrogenase 2 (11 $\beta$ HSD2), which inactivates cortisol and facilitates aldosterone's specificity of action at the MR. In other tissues, including cardiac and adipose tissue, MR expression is present, but significant expression of 11 $\beta$ HSD2 has not been identified [25]. As cortisol circulates in concentrations approximately 1000-fold higher than aldosterone under normal physiologic conditions, cortisol is thought to be the primary agonist for the MR in these tissues, with changes in aldosterone concentration presumably of little physiologic significance. However, emerging evidence challenges this paradigm. First, numerous effects of aldosterone occur too rapidly to attribute to the classic genomic model of transcription regulation [26, 27]. These actions, which include stimulating proliferation of vascular smooth muscle cells [28] and inducing arterial vasoconstriction [29], may be mediated by non-genomic signaling through the MR or may involve a separate receptor for aldosterone that has yet to be identified. Second, animal studies suggest that

Randomized placebo-controlled trial to investigate the effects of eplerenone in patients with HIV-associated abdominal fat accumulation

glucocorticoid may act as an antagonist rather than an agonist of the MR in some tissues [30-32]. In a rodent model, infusion of aldosterone alone caused hypertension and cardiac fibrosis, whereas concomitant infusion of 30-fold corticosterone significantly attenuated the development of hypertension and fibrosis [31]. Moreover, transgenic mice that overexpress 11 $\beta$ HSD2 in cardiomyocytes, causing decreased glucocorticoid occupancy of the MR and increased signaling by aldosterone, developed cardiac fibrosis, dilated cardiac hypertrophy, and heart failure [32]. Taken together, these data suggest that aldosterone may have physiological relevance even in tissues without significant 11 $\beta$ HSD2 activity. Increasing evidence suggests that aldosterone may be increased in individuals with increased VAT and may play a significant role in lipid metabolism, glucose homeostasis, and inflammation.

***Interactions between aldosterone, mineralocorticoid receptor, and adipose tissue***

Abundant evidence suggests a bidirectional relationship between adipose tissue and aldosterone, with adipose tissue potentially increasing aldosterone levels, and aldosterone increasing adipogenesis and lipid storage in adipocytes. Regarding the effect of adipose tissue on aldosterone production, angiotensinogen production has been demonstrated in both differentiated 3T3-L1 adipocytes [33] and in human abdominal subcutaneous (SC) adipose tissue [34]. Angiotensin converting enzyme (ACE) mRNA is also present in human SC adipose tissue [34]. Further, Ehrhart-Bornstein et al. have demonstrated that secretory products from human adipocytes can stimulate mineralocorticoid steroidogenesis in human adrenocortical cells even in the presence of angiotensin receptor blockade with valsartan, suggesting that other “mineralocorticoid releasing factors” in addition to angiotensinogen may be produced by adipocyte tissue [35]. Extending on this work, this group has subsequently demonstrated that adipocyte-derived factors induce Wnt signaling and increase StAR promoter activity, increasing production of cortisol and aldosterone [36]. Further, adipocyte-derived factors also appear to sensitize human adrenocortical cells to angiotensin II, also contributing to increased aldosterone production [37]. These mechanisms may underlie the numerous reports of increased systemic aldosterone levels with increasing body fat. Twenty-four hour urine aldosterone/creatinine is higher in animal models of obesity (db/db mice) compared to lean (db/+) mice [19], and, in non-HIV populations, both 24-hour urine aldosterone and angiotensin II-stimulated aldosterone are higher in overweight and obese normotensive adults compared to lean controls [38]. Some reports suggest that the relationship of aldosterone and body fat may be largely mediated by increased VAT. Goodfriend et al. demonstrated that plasma aldosterone correlates with VAT in normotensive women [16], and, as above, we have demonstrated a positive relationship of 24-hour urinary aldosterone with VAT in HIV-infected women [18].

In addition to evidence that adipose tissue increases aldosterone production, recent studies suggest that MR activation may play an important role in adipogenesis and lipid metabolism. MRs have been identified in adipocytes from several fat depots, including both VAT and SAT from humans [25] and murine brown adipocytes [39]. Furthermore, several groups have shown that aldosterone stimulates adipocyte differentiation and increases triglyceride accumulation [40-42]. In adrenalectomized male rats, aldosterone infusion over 12 days resulted in body weight gain correlating to epididymal fat pad mass, but not to percent tissue water, suggesting that aldosterone stimulates increase in adipose tissue [43]. Notably, as 11 $\beta$ HSD2 is not highly expressed in adipocytes [25], MR activation, by either cortisol or aldosterone, may be a more relevant focus in adipose tissue than aldosterone levels per se. In this respect, MR

Randomized placebo-controlled trial to investigate the effects of eplerenone in patients with HIV-associated abdominal fat accumulation

appears to play a crucial role in adipocyte differentiation and lipid accumulation. In 3T3-L1 cells, MR but not glucocorticoid receptor (GR) downregulation by siRNAs inhibited adipocyte differentiation and decreased cell triglyceride content [44]. Furthermore, whereas murine adipocytes lacking GR show mild impairment in lipid accumulation during early differentiation, adipocytes lacking MR demonstrate failure to accumulate lipid throughout differentiation [39]. These observations are supported by *in vivo* models of ob/ob and db/db mice, in which MR blockade with eplerenone significantly decreased the number of hypertrophic adipocytes in epididymal fat [45]. Blockade of MR, which we propose to study in this grant application, would block MR activation by cortisol as well as aldosterone in adipose tissue, and may decrease lipid accumulation and ultimately affect body composition. There is also some evidence to suggest that MR blockade may affect hepatosteatosis, which is prevalent in HIV-infected individuals in association with increased abdominal adiposity [46, 47]. In a murine model of diet induced obesity, Wada et al. demonstrate that spironolactone significantly decreases hepatic triglyceride accumulation as well as decreasing serum triglyceride, total cholesterol, and free fatty acid [20]. In humans, Fallo et al. demonstrate an increased prevalence of hepatosteatosis in patients with primary aldosteronism (PA) compared to normotensive controls, but the prevalence in PA (57.5%) was not different from the prevalence found in a matched cohort with low-renin essential hypertension (55.8%) [48]. Further studies are clearly needed to determine whether mineralocorticoid activity affects hepatic triglyceride accumulation. Aim I of the current proposal will investigate relationships between aldosterone level and body fat distribution, including ectopic fat storage in liver.

***Aldosterone, Mineralocorticoid Receptor, and Insulin Resistance***

Multiple epidemiologic studies have found positive associations between aldosterone and markers of insulin resistance in overweight and obese patients [16, 17, 38, 49], hypertensive patients [49], and patients with heart failure [50]. Moreover, a high prevalence of impaired glucose tolerance has been recognized in primary aldosteronism (PA) for several decades [51]. In recent series, patients with PA are generally reported to have impaired glucose homeostasis in comparison to both controls and patients with essential hypertension [52, 53], although one recent study refutes this association [54]. Further, treatment of PA with either surgery or aldosterone antagonism improves glucose homeostasis in this population [52]. Genetic polymorphisms in aldosterone synthase have also demonstrated an association with both fasting glucose and glucose following OGTT, which further suggests a possible relationship between aldosterone and glucose homeostasis [55].

Although impaired insulin secretion secondary to hypokalemia is one likely cause of impaired glucose homeostasis in hyperaldosteronism, *in vitro* and animal studies have demonstrated additional mechanisms linking aldosterone directly to glucose homeostasis. Hitomi et al., using vascular smooth muscle cells from rat aorta, demonstrate that aldosterone dose-dependently decreases insulin receptor substrate-1 (IRS-1), prevents insulin-induced Akt phosphorylation, and reduces insulin-stimulated glucose uptake [56]. Notably, all of these effects are reversed with addition of eplerenone to achieve MR blockade [56]. Wada et al. demonstrate similar effects of aldosterone to reduce IRS-1 and IRS-2, decrease Akt phosphorylation, and decrease glucose uptake in 3T3-L1 adipocytes [57]. In their model, however, glucocorticoid antagonism with RU486 but *not* MR antagonism with eplerenone reversed the effects of aldosterone, suggesting possible action through the GR rather than the MR [57]. Another potential mechanism has been demonstrated *in vivo* using Wistar rats, in which

Randomized placebo-controlled trial to investigate the effects of eplerenone in patients with HIV-associated abdominal fat accumulation

aldosterone treatment significantly decreased glucose uptake in muscle and liver in conjunction with decreased GLUT4 protein expression in muscle and decreased GLUT2 protein expression in liver [58], suggesting that aldosterone may directly contribute to insulin resistance at the level of the liver and the muscle. *In vivo* rodent models also demonstrate beneficial effects of mineralocorticoid blockade on glucose homeostasis. Hirata et al. demonstrate that eplerenone treatment of ob/ob and db/db mice significantly reduced glucose and HOMA-IR [45], and Guo et al. also describe decrease in HOMA-IR in db/db mice treated with eplerenone [19]. Wada et al. demonstrate similar results in a murine model of diet induced obesity, with improved response to both glucose tolerance test and insulin tolerance test following treatment with spironolactone [20]. Taken together, these data strongly support a relationship between mineralocorticoid activity and glucose homeostasis and suggest that mineralocorticoid blockade may be a useful strategy to improve glucose homeostasis in models of increased adiposity.

**Mineralocorticoid receptor and subclinical inflammation**

HIV-infection is accompanied by increased markers of systemic inflammation [12-14], and levels of inflammatory cytokines predict atherosclerosis [6, 59] and myocardial infarction [60] in HIV-infected individuals. In addition to the recognized role of angiotensin II to stimulate production of reactive oxidant species [61, 62], recent studies suggest that MR activation may play a distinct role in both cardiovascular and systemic inflammation. In Sprague-Dawley rats, aldosterone administration for 4 weeks produced significant medial thickening of coronary arteries as well as perivascular leukocyte infiltration and, in some animals, significant leukocyte infiltration into cardiac tissue with subsequent cardiomyocyte degeneration and necrosis [63]. These changes were accompanied by increased gene expression of cyclooxygenase-2 (COX-2), macrophage chemoattractant protein-1 (MCP-1), osteopontin, and ICAM-1. Concomitant eplerenone treatment significantly ameliorated inflammatory changes and attenuated alterations in gene expression [63]. Although a role of hypertension cannot be excluded in this model, a model of atherosclerosis-prone apoE deficient mice supports the association between MR activation and vascular inflammation, independent of blood pressure. Six weeks of high-cholesterol diet in these mice led to formation of atherosclerotic lesions in the aorta, with increased superoxide production and increased vascular expression of NADPH oxidase, TNF $\alpha$ , MCP-1 [64]. Eplerenone treatment did not alter total cholesterol levels or blood pressure, but significantly reduced atherosclerotic lesion area and decreased superoxide production as well as expression of NADPH oxidase, TNF $\alpha$  and MCP-1 [64]. Moreover, although treatment with valsartan alone also had beneficial effects to decrease lesion area and reduce oxidative stress, the combination of valsartan and eplerenone was significantly more effective than valsartan alone to reduce atherosclerotic area and oxidative stress, suggesting an effect of MR blockade distinct from that of ATII blockade [64]. Similar results have been reported in a rabbit model, with eplerenone treatment significantly improving endothelial function and decreasing superoxide production and NADPH oxidase activity in aorta of animals fed a high-lipid diet [65]. Taken together, these animal data suggest a direct effect of MR activation on oxidative stress, endothelial function, and atherosclerotic changes in the vasculature.

Effects of aldosterone on adipocyte inflammation and on systemic levels of inflammation have also been demonstrated. Aldosterone has also been shown to contribute to angiotensin-II induced increase in C-reactive protein (CRP) [66], and aldosterone stimulation of adipose tissue increases mRNA expression of IL-6 and PAI-1

## Randomized placebo-controlled trial to investigate the effects of eplerenone in patients with HIV-associated abdominal fat accumulation

[39]. Further, aldosterone increases LDL-oxidation in human vascular smooth muscle cells [67]. Evidence that MR blockade ameliorates inflammation confirms that inflammatory actions of aldosterone occur via the MR. Eplerenone treatment in angiotensin II-infused, hypertensive rats decreases both serum and urinary CRP [66]. As described further in our preliminary data, MR blockade by treatment with eplerenone in obese db/db mice markedly reversed obesity related increases in mRNA expression of TNF- $\alpha$  and other inflammatory markers locally in retroperitoneal adipose tissue and increased adiponectin mRNA expression [19]. Similarly, Hirata et al. describe numerous effects of eplerenone in adipose tissue of ob/ob and db/db mice [45]. Significantly, they report that MR mRNA levels in adipose tissue were significantly increased in ob/ob and db/db mice compared to lean controls, supporting a key role for MR in adipocyte biology. Eplerenone treatment in these mice significantly reduced reactive oxygen species and decreased mRNA expression of NADPH oxidase subunits [45]. Further, in ob/ob mice, eplerenone reduced mRNA expression of MCP-1, IL-6, and TNF $\alpha$  [45]. Similar effects were reported in a diet-induced obesity mouse model, in which spironolactone resulted in significant decreases in hepatic expression of TNF $\alpha$ , IL-6, and MCP-1 [20]. Given this abundant animal data, research is greatly needed into the effects of aldosterone and MR blockade on systemic and local inflammation in humans. In this study we will carefully study the effects of MR blockade on systemic inflammation and endothelial function in HIV-infected individuals, with the hypothesis that MR blockade will have beneficial effects to reduce systemic inflammatory markers and improve endothelial function in this population with increased risk of atherosclerosis and CV morbidity.

### **Conclusion**

Despite the critical need to reduce CVD risk in HIV-infected patients, a comprehensive and effective strategy has not yet been developed to accomplish this purpose. Indeed, numerous strategies have been tried with varying degrees of success to improve the metabolic and cardiovascular abnormalities in HIV-infected patients. Lifestyle modification (LSM) strategies have demonstrated a substantial benefit to reduce CVD risk factors among HIV-infected patients. We have previously demonstrated positive effects of a well designed, achievable LSM program on HDL, waist circumference and HgbA1c [68]. Based on our data, we maintain that LSM should be the foundation of any treatment strategy. As shown in our preliminary data and in other studies using this strategy, however, LSM is unlikely to reverse completely the metabolic abnormalities associated with HIV [68], [69], [70], [71].

In summary, epidemiologic studies have established that aldosterone is increased in association with increased BMI, and some evidence suggests that VAT in particular may be related to increased aldosterone. *In vitro* and animal data demonstrate a cross-talk between aldosterone/MR and adipose tissue, such that increased adiposity may increase aldosterone, and MR activation may, in turn, increase adipocyte differentiation and triglyceride accumulation. Further, increasing research demonstrates a role for MR activation in glucose homeostasis, inflammation, and atherosclerosis. Lo et al. [18] demonstrated increased aldosterone levels in association with increased VAT in HIV-infected women. MR activation may be a mediator of some of the detrimental effects of excess visceral adiposity in HIV, and MR blockade may provide to be an important element of a larger strategy to reverse endocrine abnormalities, improve insulin sensitivity, and decrease inflammation in HIV.

Evidence suggests that MR blockade may have beneficial effects on cardiovascular and metabolic parameters, and the selective MR blocker eplerenone has

## Randomized placebo-controlled trial to investigate the effects of eplerenone in patients with HIV-associated abdominal fat accumulation

proven safe and effective in non-HIV infected populations with cardiovascular disease. Our preliminary data suggest increased aldosterone in HIV-infected individuals with increased abdominal adiposity, a population with significant risk of insulin resistance and cardiovascular morbidity and for whom no specific treatment is currently available. MR blockade with eplerenone may be one beneficial strategy to address impaired glucose homeostasis and cardiovascular risk in this group, but the effects of eplerenone in HIV-infected individuals with abdominal fat accumulation and impaired glucose tolerance are not known. We hypothesize that by blocking the effects of increased aldosterone secretion, eplerenone treatment will significantly improve insulin sensitivity in this population and may also decrease visceral adipose tissue, and improve dyslipidemia and inflammation, thereby improving vascular function. In a 6-month, randomized, placebo-controlled study followed by 6-month open-label extension, we will test for the first time the effects of the selective mineralocorticoid blocker, eplerenone, on markers of insulin sensitivity, dyslipidemia, body composition, inflammation and vascular function in this population.

Eplerenone was chosen for this study instead of an ACE-I or Angiotensin II Receptor Blocker (ARB) because we want to specifically test the effects of MR blockade, including in tissues in which cortisol may activate the MR due to lack of significant 11 $\beta$ HSD2 expression. Evidence suggests that MR activation in adipose tissue may affect adipocyte differentiation and triglyceride accumulation, and cortisol may act similarly to aldosterone at the MR in this regard. As we aim to determine the effects of MR blockade on cardiometabolic parameters and body composition, specifically VAT accumulation, we have chosen eplerenone in order to block the effects of both aldosterone and potentially cortisol at the MR. Eplerenone was chosen rather than spironolactone because eplerenone is more selective for the MR, does not affect adrenal steroid synthesis as spironolactone does, and has a better side effect profile.

### II. Specific Aims

To determine if mineralocorticoid receptor blockade with eplerenone among HIV-infected patients with increased waist circumference and impaired glucose tolerance will ameliorate cardiovascular risk parameters, we will perform a randomized double-blind study of eplerenone vs. placebo for 6 months, with a 6 month safety extension. We will provide all subjects with lifestyle modification throughout the study. We hypothesize that addition of eplerenone to lifestyle modification will significantly:

- A. Improve insulin sensitivity as measured by euglycemic hyperinsulinemic clamp.
- B. Improve endothelial function and adipokines.
- C. Reduce critical measures of adiposity, including liver fat and IMCL

### III. Subject Selection

#### Inclusion/Exclusion:

##### Inclusion criteria:

1. Increased waist circumference based on NCEP guidelines (>102cm in men and >88cm in women) and impaired glucose tolerance (either IFG > 100 mg/dL but < 126 mg/dL or 2hr glucose > 140 mg/dL but < 200 mg/dL, or fasting insulin >12  $\mu$ IU/mL)
2. HIV positive for 5 years and on a stable ART regimen for at least 12 months
3. Age  $\geq$  30 and  $\leq$  65 years of age

Randomized placebo-controlled trial to investigate the effects of eplerenone in patients with HIV-associated abdominal fat accumulation

4. Stable CD4 count and HIV viral load in the past year

Exclusion criteria:

1. ACE Inhibitor, ARB, verapamil, or spironolactone
2. Potassium supplementation
3. Estimated GFR<60, creatinine > 1.5 mg/dL
4. Serum K > 5.5 mEq/L, ALT > 2.5 times the upper limit of normal, Hgb < 11g/dL
5. Uncontrolled hypertension (SBP  $\geq$  160 or DBP  $\geq$  100)
6. Current or prior steroid use within past 6 months
7. Known history of diabetes mellitus or current use of anti-diabetic medications
8. Concomitant use of full dose ritonavir, nelfinavir, clarithromycin and other strong inhibitors of CYP3A4
9. Use of St. John's Wort (CYP3A4 inducer)
10. For women: Pregnant or actively seeking pregnancy, breastfeeding, failure to use an acceptable non-hormonal form of birth control, including abstinence, barrier contraceptives, or non-hormonal IUD.
11. Estrogen or progestational derivative use within 3 months
12. Testosterone use for non-physiologic purposes, or physiologic testosterone replacement for < 3 months.
13. Current growth hormone or growth hormone releasing hormone use
14. Current viral, bacterial or other infections (excluding HIV)
15. Current active substance abuse
16. Patients with a significant history of cardiovascular disease, including prior MI or stroke

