## **V. Study Procedures**

### Data Collection/Study Procedures

#### *Screen Visit (to determine eligibility)*

1. Informed consent; history and PE, vital signs including blood pressure, and urine pregnancy test for all female subjects
2. Bionutrition: Height, metabolic weight, and anthropometric measurements, including waist and hip circumferences, distribution of a 4-day food record
3. Fasting blood: potassium, creatinine, CBC, ALT, FSH (women only)
4. 2 hour oral glucose tolerance test

Prior to the baseline, 3, 6 and 12 month visits, subjects will go on a uniform 200 meq/day sodium diet.

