#### 3 Month Visit

1. Urine pregnancy test for all female subjects
2. Physical exam, including blood pressure check, and medical history

Randomized placebo-controlled trial to investigate the effects of eplerenone in patients with HIV-associated abdominal fat accumulation

3. Euglycemic hyperinsulinemic clamp
4. Bionutrition: DEXA, anthropometric measurements, and review of a session from the lifestyle modification workbook.
5. Fasting blood: lipid profile, HgbA1c, chem. 7, CBC, potassium, creatinine, ALT, CD4/8, viral load, aldosterone, plasma renin activity, inflammatory markers and adipokines: MCP-1, CRP, adiponectin, PAI-1, resistin, TNF $\alpha$ , TNFR2, IL-6, SHBG, total and free testosterone, LH, FSH, estradiol (females only).
6. 24 hour urine will be collected for aldosterone, potassium, sodium, cortisol, and creatinine
7. Optional overnight q 20 minute sampling for growth hormone pulsatility analysis
8. Modifiable activity questionnaire

Oral Glucose Tolerance Test: A standard 75g OGTT will be performed on the morning of the screen visit following a 12 hour fast, with interval measurements of insulin and glucose at 0 and 120 min.

Euglycemic-Hyperinsulinemic Clamp: After 12-h overnight fast, patients will receive a primed infusion of regular insulin mixed with albumin, 80 mU/m^2, for 2 hours, with a variable rate of dextrose administered to maintain blood glucose at 5.0 mmol/L (90 mg/dL). Blood samples will be collected for glucose at time 0 and every 5 min during the 2-hour clamp, and samples for insulin will be collected every 20 min from 0-120 minutes. Insulin sensitivity will be calculated.

Optional GH Pulsatility Analysis: Starting at 2000 until 0740 the next morning, fasting blood will be sampled every 20 minutes. Approximately 1.5cc of blood will be drawn at each time point for a total of 54cc. Mean overnight GH concentration, basal concentration, pulse frequency, pulse amplitude and overall pattern regularity will be determined using the deconvolution analysis and cluster computerized pulsatility program.

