Hyperkalemia is a potential side effect of eplerenone use, and contraindications for the use of eplerenone include serum K > 5.5 mEq/L at initiation. Therefore, any subject with serum K > 5.5 mEq/L at screen will be excluded from the study. During the study, a subject who has an elevated K of > 5.5 mEq/L at any study visit will have a recheck; if the K remains elevated after recheck they will be excluded from the study. Additionally, subjects who experience symptoms of hyperkalemia and have a K > 5.0 mEq/L will be excluded from continued participation in the study. Subjects who have hypotension (SBP < 90) at any study visit after titration to full dose eplerenone 50mg/d will be given a dose reduction to 25 mg/d. If a subject remains hypotensive (SBP < 90) or symptomatic of hypotension at the reduced dose they will be dropped from the study. Since patients with renal insufficiency may require reduced dosing based on creatinine clearance, subjects with renal insufficiency (serum creatinine > 1.5 mg/dl) will also be excluded from participation. Other side effects have been reported and include dizziness, fatigue, diarrhea, headache, stomach pain, cough, breast enlargement or breast enlargement, rash, abnormal vaginal bleeding. Rare but serious side effects include chest pain, tingling in arms and legs, loss of muscle tone, weakness or heaviness in legs, confusion, lack of energy, cold, gray skin or irregular heartbeat. These potential side effects will be assessed for throughout the study.

Exclusion criteria during the study include use of diabetic agents; initiation of ACE-I, ARB, or spironolactone; Hgb < 11; ALT > 2.5 x ULN; persistent hyperkalemia (K > 5.5 mEq/L despite recheck and/or symptoms of hyperkalemia if K > 5.0 mEq/L). If a subject remains hypotensive (SBP < 90) or symptomatic of hypotension after a dose reduction of eplerenone to 25mg for this same reason during the study, they will be dropped from the study.

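### Inclusion criterion 1 applies each upper glucose limit only to its own route of entry, so a subject above one limit at screening can still qualify by another route

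*Combined protocol and SAP*

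**What the plan says.** - **Inclusion criterion 1** (III. Subject Selection) requires a raised waist circumference together with impaired glucose tolerance. It defines the latter as "either IFG > 100 mg/dL but < 126 mg/dL or 2hr glucose > 140 mg/dL but < 200 mg/dL, or fasting insulin >12" µIU/mL.
- **Exclusion criterion 7** (same section) is the only exclusion that concerns diabetes: "Known history of diabetes mellitus or current use of anti-diabetic medications". No exclusion sets a maximum screening glucose.
- **II. Specific Aims** names the study population as having increased waist circumference and impaired glucose tolerance.
- **V. Study Procedures** lists a "2 hour oral glucose tolerance test" at the screen visit. The test description adds that it is done "with interval measurements of insulin and glucose at 0 and 120 min". Every value needed to apply the limits is thus in hand before randomization, which takes place at the baseline visit.
- **IV. Subject Enrollment** requires all criteria to be met, and requires the primary care physician to be consulted before randomization. Neither statement adds a glucose limit.
- **IX. Monitoring and Quality Assurance**: "Exclusion criteria during the study include use of diabetic agents".

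**The concern.** Upper limits of 126 and 200 mg/dL serve little purpose if a subject who exceeds one of them can enter through another route. They suggest that the plan meant to enrol people with impaired glucose tolerance and to stop there. As written, the rule does not do this. The word known in exclusion 7 leaves out anyone whose high value first appears at the screening test.

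Two things are at stake:

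- **Population.** Some entrants may lie outside the population that the aims describe.
- **Missing primary data.** The primary endpoint is the change in insulin-stimulated glucose uptake on the clamp, measured at baseline, 3 and 6 months. A subject with a high screening glucose may be put on a diabetic agent, and section IX then ends participation. Clamps due after that date would be missing because of the subject's glycemia, which is closely related to the endpoint.

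**Working it through.** **Inputs.** F is fasting glucose (mg/dL), G is 2-hour glucose (mg/dL) and I is fasting insulin (µIU/mL). All thresholds come from inclusion criterion 1.

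- Route A, "either IFG > 100 mg/dL but < 126 mg/dL or": 100 < F < 126
- Route B, "or 2hr glucose > 140 mg/dL but < 200 mg/dL": 140 < G < 200
- Route C, "or fasting insulin >12": I > 12

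**Step 1. The rule as written.** The glycemic part of the criterion is met if A or B or C is true. Exclusion 7 acts on history and current medication, not on F or G, so it does not alter this result for a subject without a prior diagnosis.

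**Step 2. Test the rule.** Take F = 90, 110, 130; G = 120, 170, 210; I = 8, 15. That gives 3 × 3 × 2 = 18 profiles, chosen to fall on either side of each limit. Of these, 14 meet the rule and 4 do not.

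Ten of the 18 have F or G above an upper limit: all six with F = 130, and the four with G = 210 and F = 90 or 110. They divide as follows.

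| F / G / I | Enters? | Route |
|---|---|---|
| 110 / 210 / 8 | yes | A |
| 110 / 210 / 15 | yes | A, C |
| 90 / 210 / 15 | yes | C |
| 130 / 170 / 8 | yes | B |
| 130 / 170 / 15 | yes | B, C |
| 130 / 120 / 15 | yes | C |
| 130 / 210 / 15 | yes | C |
| 90 / 210 / 8 | no | none |
| 130 / 120 / 8 | no | none |
| 130 / 210 / 8 | no | none |

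Seven enter and three do not. A value above a limit does not itself admit anyone; another route has to be met. The profile 130 / 210 / 15 is above both glucose limits and still enters, on insulin alone.

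**Step 3. The rule with the plan's own limits applied throughout.** Require (A or B or C) and F < 126 and G < 200. The number of eligible profiles falls from 14 to 14 − 7 = 7. The seven that drop out are exactly the seven marked yes above.

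**Step 4. The plan's power figure.** The Sample Size Calculation states 80% power for 0.8 SD with 25 evaluable per group at P = 0.05 (taken as two-sided). The noncentrality is 0.8 / √(2/25) = 2.83. The normal approximation gives Φ(2.83 − 1.96) = 80.7%, and the noncentral t with 48 degrees of freedom gives 79.1%, so the figure reproduces. It is not an input to Steps 1 to 3. Moving from the eligibility rule to a change in power would need the share of entrants above a limit, the share of those who start a diabetic agent, and the timing. The documents give none of these.

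**The case against.** **The criterion can be read for its evident purpose.** Its governing term is impaired glucose tolerance, the limits show what is meant, and the screening values and the primary care consultation both precede randomization. An investigator might well turn away a subject with a 2-hour value of 210. This has some force: the intent is fairly clear, and the documents nowhere label values of 126 or 200 and above as diabetes, so the inference rests on the limits alone. But the bracketed text is the only working definition of the term, exclusion 7 does not say that a screening result counts as known history, and the consultation carries no glucose limit. The defense depends on staff reading in a limit that is not written, and they may not all do so alike.

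**The loss of data may be small.** VI. Biostatistical Analysis keeps all interim data from non-completers in the mixed model. A removed subject therefore still contributes clamps already done, and missingness that those measured values explain is handled to that extent. This stands. What the model cannot recover is the later clamps themselves, or a removal that depends on values not observed. The planned last-observation-carried-forward analysis does not address that mechanism.

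**A reader might infer a loss of power from added variance.** If a share f of entrants had uptake lower by d SD, the SD of the level would rise by √(1 + f(1 − f)d²). With assumed values f = 0.04, d = 1 the factor is 1.02, and with f = 0.16, d = 2 it is 1.24. Put into the power formula, these give 77.6% and 60.8%. The documents do not support that reading. The endpoint is change, and a constant shift in a subject's level cancels from the difference between two visits. Percent change, which the sample size paragraph uses, could be affected through a smaller denominator, but nothing in the documents allows that to be sized. Both f and d are also pure assumptions.

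**A reader might also subtract removed subjects from 25 per group.** Losing 1, 2 or 3 per arm would give 77.4%, 75.6% or 73.6%. But the plan's 25 are already evaluable patients, and no enrolment number is stated. Those figures describe attrition in general and not this criterion.

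**Conclusion.** The concern holds as a defect in the written eligibility rule. A subject above one of the criterion's own glucose limits at screening can qualify through another route, and neither exclusion 7 nor the enrolment text prevents it. In the illustrative grid this applies to 7 of the 10 profiles above a limit, or 7 of 18 overall. These counts show how the rule behaves and say nothing about how often it would happen.

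Three limits apply. It would be too strong to say that everyone with a high screening value qualifies, since three of the ten do not. It would be too strong to say that the enrolled population is not the stated one; at most, some entrants may fall outside it. The path from entry to treatment, removal and missing clamp data is possible under section IX, but no step in it has a documented rate. No effect on power, variance or bias can therefore be given.

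The conclusion assumes that the three routes are read as alternatives, which is what the wording says, and that the upper limits were meant to define the population, which is inferred from their presence and from II. Specific Aims.

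**What to change.** Reconcile II. Specific Aims, inclusion criterion 1, exclusion criterion 7 and the on-study exclusions in section IX by stating that the plan's own upper limits apply to every route of entry. Inclusion criterion 1 could require, for all subjects at the screening OGTT, fasting glucose < 126 mg/dL and 2-hour glucose < 200 mg/dL, plus at least one of fasting glucose > 100 mg/dL, 2-hour glucose > 140 mg/dL or fasting insulin > 12 µIU/mL. Exclusion 7 should then say how a value found at screening is treated, so that the two criteria agree. If the sponsor did mean to admit subjects above a limit, the aims should describe that population instead.

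The cost is a short eligibility amendment and some additional screen failures, whose number cannot be estimated from the documents. No new measurement is needed, because glucose and insulin at 0 and 120 minutes are already taken at screening. The change does not remove all outcome-related loss: a properly eligible subject who later starts a diabetic agent would still fall under section IX.
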